Official Title: Investigating the Immunomodulatory Effects of Esmolol in Sepsis Management and Its Impact on Patient Outcomes

NCT Number: Pending

Study Duration: January 2020 to December 2021.

Funding Source:

Sichuan Provincial Healthcare Commission - Popularization Application Project (21PJ081); and the Sichuan Cadre Healthcare Scientific Research Project (General Subject Program) (Sichuan Cadre Research 2021-207).

Principal Investigator: [name]

Affiliation: Sichuan Provincial People's Hospital

Address: [name]

Contact Information:

Email: [contact]

[contact]

Document Date: March 2, 2024

Study Protocol

Title: Esmolol in Sepsis Management: Evaluating Immunomodulatory Effects and Impact on Patient Outcomes

Objective: Evaluate the effectiveness of esmolol, a selective β 1-adrenergic receptor blocker, in modulating immune responses and improving patient outcomes in sepsis.

Background: Sepsis remains a significant challenge in intensive care with high mortality rates and complex pathophysiology involving the immune system and sympathetic nervous system (SNS) interactions. This study investigates the efficacy of esmolol in modulating immune responses and improving patient outcomes in sepsis.

Methodology:

- **Study Design:** Single-center prospective controlled study comparing patient groups treated with either standard care or standard care plus esmolol based on clinical suitability and heart rate levels.
- **Participants:** 105 patients diagnosed with sepsis or septic shock, admitted to the MICU/RICU of Sichuan Provincial People's Hospital from January 2021 to December 2022, with informed consent obtained.
- **Procedures:**
 - Random assignment of patients to treatment groups.
 - Continuous monitoring and adjustment of esmolol dosage to maintain target heart rate.
 - Collection of data on inflammatory markers, immune function, hemodynamics, and clinical outcomes.
- **Ethics Approval:** Granted by the Ethics Committee of Sichuan Provincial People's Hospital.

Statistical Analysis Plan

- **Data Analysis Strategy:**
 1. Descriptive Statistics: Summarize participant characteristics using means \pm standard deviations for continuous variables and frequencies for categorical variables.

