 2. Effectiveness Evaluation: Perform logistic regression to evaluate the impact of esmolol on survival rates and clinical outcomes. Kaplan-Meier survival analysis with Log-rank test for comparing survival rates between treatment groups.
 3. Comparison Between Groups: Use independent samples t-tests or Mann-Whitney U tests for continuous variables and chi-square tests for categorical variables to compare the esmolol and control groups across different measures.
 4. Correlation Analysis: Assess the relationship between baseline immune function markers and treatment response using Pearson's or Spearman's correlation coefficients, depending on data distribution.

Software: Statistical analysis will be conducted using SPSS version 25.0 or a similar statistical package.

Ethical Considerations: Data will be anonymized to protect patient confidentiality, with all procedures carried out in accordance with the Declaration of Helsinki.

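### Heart-rate level is named as a basis for giving esmolol, yet no stated group comparison conditions on entry heart rate: confounding if it influenced allocation, a modest loss of efficiency if patients were randomised

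*Protocol*

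**What the plan says.** The Methodology section describes allocation in two ways. Study Design says the groups receive "standard care or standard care plus esmolol based on clinical suitability and heart rate levels". Procedures lists "Random assignment of patients to treatment groups", with no ratio, method or stratification factor. The sample is "105 patients diagnosed with sepsis or septic shock"; group sizes are not given.

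The section headed Statistical Analysis Plan then fixes the comparisons:

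- Item 2, survival: "Kaplan-Meier survival analysis with Log-rank test for comparing survival rates between treatment groups", with no stratum named.
- Item 2, survival and clinical outcomes: "Perform logistic regression to evaluate the impact of esmolol on survival rates and clinical outcomes", with no covariate named.
- Item 3, all other group contrasts: "Use independent samples t-tests or Mann-Whitney U tests for continuous variables and chi-square tests for categorical variables".
- Item 4 is the only analysis that uses a baseline variable: "Assess the relationship between baseline immune function markers and treatment response". It is a correlation, not a group contrast, and it does not involve heart rate.

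Procedures also includes "Continuous monitoring and adjustment of esmolol dosage to maintain target heart rate". On-treatment heart rate is therefore steered by the drug and is a different quantity from heart rate at entry.

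**The concern.** Entry heart rate is the one measurable quantity that the protocol ties to receiving esmolol, and it enters none of the stated comparisons. The protocol's background describes sepsis in terms of interaction between the immune and sympathetic nervous systems, so it is plausible that entry heart rate relates to both survival and immune markers. If the groups differ in entry heart rate for that reason, the planned tests would attribute the resulting difference to esmolol.

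The direction of the error matters. If esmolol went to patients with faster heart rates, and faster rates go with worse outcome, the bias would suggest harm or hide a real benefit. The reverse pattern would create an apparent benefit. Either way it bears on the trial's stated objective.

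**Working it through.** **Plan's own figure.** The only figure is the total of 105. No error rate, power, effect size, event rate or allocation ratio accompanies it, so it cannot be reproduced. The calculations below use it only as the sample size, split 52 + 53 = 105 by assumption.

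**Other inputs, all assumed.** The protocol gives none of these: 35% average mortality; mortality odds multiplied by 1.5 or 2 per SD of entry heart rate; a marker correlated 0.3 with entry heart rate; group means of heart rate d = 0.5 or 1 SD apart; no true esmolol effect.

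**Mortality.** Let x be standardised entry heart rate, normal with SD 1 and mean +d/2 in one group and −d/2 in the other. Take logit P(death) = a + ln(OR)·x, with a chosen so that the two group mortalities average 35%. The rejection rate is that of the pooled two-proportion z-test (equivalent to the chi-square test), found by summing the exact binomial probabilities.

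| OR per SD | d | Expected mortality | Rejection rate, nominal 5% |
|---|---|---|---|
| 1.5 | 0.5 | 37.2% v 32.8% | 7.3% |
| 2.0 | 0.5 | 38.6% v 31.4% | 11.4% |
| 1.5 | 1 | 39.4% v 30.6% | 15.2% |
| 2.0 | 1 | 42.1% v 27.9% | 32.3% |

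Hand check of the third row by normal approximation: SE = √(0.394×0.606/52 + 0.306×0.694/53) = 0.093. The difference of 0.089 gives 0.089/0.093 = 0.96, and P(Z > 1.96 − 0.96) + P(Z < −1.96 − 0.96) ≈ 16%. With a pooled null SE, the approximation gives 7.6%, 11.9%, 15.8% and 33.0% for the four rows, within about one point of the exact values. With d = 0 the test keeps its level.

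**Markers.** The spurious shift is r × d, and the noncentrality is r·d/√(1/52 + 1/53), where the root is 0.195. For d = 0.5: 0.15/0.195 = 0.77, and the t-test on 103 df rejects 12%. For d = 1: 0.30/0.195 = 1.54, and it rejects 33%.

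**Simulation check.** This used 105 patients, mortality near 40%, 1,500 runs per setting, log hazard ratio 0.2 to 0.6 per SD of heart rate, and marker correlations of 0.20, 0.38 and 0.54.

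- *Allocation dependent on heart rate, no true effect.* With log-odds of esmolol of 1 per SD, the unadjusted log-rank rejected in 8 to 32% of runs; with 2 per SD, in 11 to 63%. Unadjusted marker comparisons rejected in 13 to 94% across both. Adjusting for entry heart rate brought logistic regression to 4.5 to 6.3% and the marker model to 3.1 to 6.1%. The implied imbalances are large: the false marker difference divided by the correlation is about 0.32/0.38 = 0.8 SD and 0.47/0.38 = 1.2 SD.
- *Random allocation.* The unadjusted log-rank rejected in about 6% of runs, so there was no bias. Adjustment cut the variance of the marker contrast by about 2 to 27%. Logistic power for a true hazard ratio of 0.5 went from 0.478 to 0.477, 0.468 to 0.473 and 0.445 to 0.488 as prognostic strength rose.

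**The case against.** The strongest reply is that the root defect is the conflict between the two allocation statements, and that the bias exists only if the Study Design wording describes how patients were allocated. That stands, and the conflict must be resolved. But resolving it does not change items 2 and 3 of the analysis section, which still leave entry heart rate out.

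A second reply is that covariate lists are commonly left to a separate statistical analysis plan. This stands for the logistic regression: naming no covariate does not exclude one, and that silence alone is no finding. It is weaker for item 3 and the log-rank, where the protocol itself chooses tests that are unadjusted as written.

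Four stronger readings may tempt a reader, and the protocol does not support them.

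- *The results are biased.* The protocol does not establish that heart rate decided allocation, gives no heart-rate entry criterion, and reports no imbalance. The 1 SD figures illustrate a large imbalance; at 0.5 SD the inflation is much smaller.
- *The point has equal force under randomisation.* It does not. The tests are then valid and the survival gain is 0 to 4 percentage points of power. Nor does the logistic model gain precision: in the randomised simulation with strong prognosis its SE rose from 0.429 to 0.462, and its odds ratio became conditional.
- *The log-rank cannot account for heart rate.* A stratified log-rank can; the plan simply names no stratum.
- *Adjustment cures non-random allocation.* It does not remove selection by clinical suitability. If a strict heart-rate cut-off decided treatment, there would be no overlap on which to adjust.

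**Conclusion.** The point holds in conditional form. No stated group comparison conditions on the one measured variable that the protocol links to receiving esmolol.

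If that variable influenced allocation, the survival and marker contrasts are confounded by it. The error rate then depends on an unknown imbalance and an unknown prognostic strength: from barely above nominal at 0.5 SD with weak prognosis to about a third at 1 SD with strong prognosis. If patients were randomised, validity is not in question and only modest efficiency is lost, mainly for markers.

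The change is worth making because it is cheap and serves under either reading. It is not evidence that any result is wrong. It also assumes that pre-treatment heart rate was recorded; the protocol lists hemodynamic data without saying when they were taken.

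**What to change.** 1. Reconcile the Study Design and Procedures statements on how patients came to receive esmolol.
2. Confirm that heart rate before treatment was recorded, and tabulate it by group. Do not use the on-treatment value, which esmolol dosing steers.
3. Prespecify pre-treatment heart rate as a continuous covariate in the item 2 logistic model. Beside the Kaplan-Meier curves, report a Cox model with the same covariate, or a log-rank stratified by heart rate. For markers and other continuous measures in item 3, use linear models that include it, on the log scale where skewed. Keep the unadjusted tests as supportive.
4. If allocation was random, keep all randomised patients. Only if it was not, restrict the comparison to the heart-rate range that the groups share, state that selection by clinical suitability remains, and limit the conclusion to an association. If there is no shared range, say that the adjusted comparison cannot be made.
5. The document is dated March 2, 2024, after both study periods that it states. If outcomes have already been examined, say so and label the adjusted models accordingly.

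The cost is plan wording and a few extra models. The adjusted odds and hazard ratios are conditional on heart rate and must be described that way. Under non-random allocation, restriction may also remove some patients from the main contrast.

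### Immune function markers are compared between groups without adjustment for their recorded baseline values, which costs precision on the first-named objective

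*Protocol*

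**What the plan says.** The Objective in the Study Protocol is to evaluate esmolol "in modulating immune responses and improving patient outcomes in sepsis", so immune modulation comes before patient outcomes. The Procedures list includes "Collection of data on inflammatory markers, immune function, hemodynamics, and clinical outcomes", and the Participants entry gives "105 patients diagnosed with sepsis or septic shock".

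Item 3 of the Statistical Analysis Plan section sets the between-group method: "Use independent samples t-tests or Mann-Whitney U tests for continuous variables", with chi-square tests for categorical variables, "to compare the esmolol and control groups across different measures". It does not say whether the tested quantity is the follow-up value or the change from baseline.

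Item 4 is the only place where baseline values appear: "Assess the relationship between baseline immune function markers and treatment response". The one regression in the section, in item 2, is logistic; it concerns survival and clinical outcomes and does not mention immune markers.

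**The concern.** A continuous immune function marker can only fall under item 3, and item 3 names nothing but unadjusted two-sample tests. The baseline value of the same marker is on file for the correlation analysis but is not used where it would help most, in estimating the effect of esmolol on that marker. Part of the between-patient variation at follow-up is already predictable from baseline. An unadjusted comparison leaves that part in the error term, so the interval is wider than the data require. It also leaves any chance baseline imbalance in the single estimate that the trial will produce.

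The point is limited to immune function markers, because these are the only measures for which the protocol documents a baseline value.

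**Working it through.** **Inputs from the protocol.** N = 105. Baseline immune function markers are recorded (item 4). The between-group tests are unadjusted (item 3). There is no power or sample-size statement, so there is no figure of the plan's own to reproduce.

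**Assumed inputs.** Two-sided alpha 0.05; 52/53 split; true difference 0.5 SD; the same SD at baseline and follow-up; baseline/follow-up correlation ρ = 0.3, 0.5, 0.7.

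**Step 1: variance of the group difference, relative to a final-value comparison.**
- Final value: 1.
- Change from baseline: 2(1 − ρ) = 1.40, 1.00, 0.60.
- ANCOVA on baseline: 1 − ρ² = 0.91, 0.75, 0.51.

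Relative to ANCOVA, the final-value comparison has variance 1/(1 − ρ²) = 1.10, 1.33, 1.96. The change-score comparison has variance 2/(1 + ρ) = 1.54, 1.33, 1.18. Both ratios exceed 1 for every ρ strictly between 0 and 1, apart from one degree of freedom. Item 3's silence on final value versus change therefore does not alter the direction.

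**Step 2: power.** Noncentral t with noncentrality d·√(n₁n₂/(n₁ + n₂)), where d is 0.5 for final values, 0.5/√(2(1 − ρ)) for changes and 0.5/√(1 − ρ²) for ANCOVA (N − 3 degrees of freedom). For final values at 52/53: 0.5 × √(52 × 53/105) = 2.56, which gives power 0.718.

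| Analysis | ρ = 0.3 | ρ = 0.5 | ρ = 0.7 |
|---|---|---|---|
| Final value, 52/53 | 0.718 | 0.718 | 0.718 |
| Change, 52/53 | 0.573 | 0.718 | 0.906 |
| ANCOVA, 52/53 | 0.758 | 0.834 | 0.944 |
| Final value, 42/42 | 0.620 | 0.620 | 0.620 |
| Change, 42/42 | 0.482 | 0.620 | 0.832 |
| ANCOVA, 42/42 | 0.660 | 0.744 | 0.887 |

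The 42/42 rows assume that 20% of patients have no follow-up value (105 × 0.8 = 84). With complete follow-up, ANCOVA gains 4 to 23 points over final values and 4 to 19 points over changes.

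**Step 3: 95% CI half-width at 52/53, in SD.** Critical t × √(1/52 + 1/53) × the square root of the relative variance in step 1. For final values: 1.983 × 0.195 = 0.387 at any ρ. For changes: 0.458, 0.387, 0.300. For ANCOVA: 0.369, 0.335, 0.276.

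**Step 4: chance imbalance.** A baseline difference of b SD shifts a final-value estimate by ρb and a change-score estimate by −(1 − ρ)b. For b = 0.3 the shifts are 0.09, 0.15, 0.21 SD and −0.21, −0.15, −0.09 SD.

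**Sensitivity.** A normal approximation with about 1:1 allocation gives 72.6% unadjusted against 76.6%, 84.1% and 94.8% adjusted. At 35/70 the same approximation gives 67.6% against 71.6%, 79.6% and 92.2%, so the pattern does not depend on an even split.

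**The case against.** The strongest reply is that nothing here is an error. The unadjusted test is valid under randomisation, the protocol makes no precision claim that it fails to meet, and covariate adjustment is often left to a separate statistical analysis plan. The first two statements are correct, and they make this a point about efficiency. The third does not settle the matter, because under its own analysis-plan heading the protocol chooses a method, and it chooses one that ignores data it records.

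Several limits on size do stand:
- Apart from N, every input to the figures is assumed. At 52/53, ANCOVA power is 72.2% at ρ = 0.1 and 73.6% at ρ = 0.2, against 71.8% for final values, a gain of 0.4 to 1.7 points (from unrounded values). If the markers correlate weakly with their baseline, little is gained over a final-value test.
- A baseline imbalance of 0.3 SD or more would occur in only about 12% of randomisations at 52/53.
- The figures are for normally distributed data and t-tests. The loss for the Mann-Whitney option on skewed data was not computed.
- The protocol names no primary endpoint. The weight given to immune markers comes from the order of the objective and from the official title.
- The protocol states both random assignment and grouping by clinical suitability and heart rate. If the second describes what happened, the unadjusted comparison is open to bias as well, and adjusting for a marker's own baseline would not remove confounding by suitability or heart rate.

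The timing objection also has force: replacing a written analysis after enrolment adds flexibility if results are known. A declaration makes that visible but does not undo it.

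**Conclusion.** The concern holds. Item 3 commits the immune function markers to a comparison that is less precise than one using their recorded baseline, whether final values or changes are tested. The direction holds for any positive correlation below 1. The size cannot be derived from the protocol: under the stated assumptions with complete follow-up, the power given up runs from 4 points to 23 (final values) or 19 (changes), and it is close to nil against final values when ρ is 0.2 or less. It is a change that should be made, not a failure of validity, and confidence in its practical importance is moderate. All of this presumes that assignment was in fact random.

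**What to change.** For each immune function marker, and for any other continuous marker that turns out to have a baseline value, make the between-group analysis a linear model of follow-up value on arm and baseline value, on the log scale if the marker is skewed. Report the adjusted difference (or ratio) with its 95% CI. Keep the t or Mann-Whitney test as supportive.

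The title block reads "Document Date: March 2, 2024", whereas patients were admitted "from January 2021 to December 2022". The change must therefore be declared as a dated departure from the planned analysis, with the reason and a statement of whether results were already known. The two allocation statements in the Methodology section need to be reconciled separately; this adjustment does not settle them.

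The cost is a short rewording of item 3 and the declaration. The model is available in the stated software and needs no new data.
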